6.1. Safety Outcomes of Concern: Rationale and Definition

With the aim of reducing potential risks associated with filgotinib, the HCP guide will address:

- Serious and opportunistic infections
- Herpes zoster
- Embryoletality and teratogenicity
- Impaired spermatogenesis
- Venous thromboembolism (VTE)
- Major adverse cardiovascular events (MACE)
- Use in the very elderly (≥ 75 years)

The summary of product characteristics (SmPC) states that patients with active tuberculosis (TB), active serious infections, or those women who are pregnant are contraindicated for treatment with filgotinib. Furthermore, patients aged 75 and older should have a starting daily dose of 100 mg as should patients with moderate or severe renal impairment (stages 3 or 4; creatinine clearance [CrCl] 15 to <60 mL/min). Screening activities include screening for TB and viral hepatitis as well as blood tests including neutrophil and lymphocyte counts, hemoglobin and lipid parameters. Further to this, the SmPC includes warnings that MACE, VTE and serious and

opportunistic infections are important safety concerns; infections are considered the main risk of immunomodulatory therapy. The following definitions are applied for these outcomes:

- MACE: Includes fatal and nonfatal CVD events. CVD comprises coronary heart disease (angina, myocardial infarction), congestive heart failure, cerebrovascular disease and peripheral artery disease.
- VTE: Includes deep venous thrombosis (DVT) and pulmonary embolism (PE).
- Serious and opportunistic infections: Opportunistic infections occur among people with weakened immune systems; such infections may be mild in people with healthy immune response but can be more serious among patients who are using immune-modulatory therapy. The overall rate of treatment-emergent serious adverse events (SAEs) at 200 mg (integrated safety summary) for serious infections was around 3.0%, among which the rate for pneumonia was 0.8%; opportunistic infections were 0.2%. The list of preferred terms in MedDRA currently comprises 192 terms under “Serious and Opportunistic infections”.

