7. RESEARCH QUESTION AND OBJECTIVES

The objectives of this study are as follows:

- To quantify the proportion of users of filgotinib being at high risk (as defined in the RMP) of developing MACE, VTE, or serious and opportunistic infections at baseline
- To quantify the proportion of filgotinib users among the very elderly (≥ 75 years) patients being initiated on filgotinib at the recommended dose of 100 mg once daily
- To quantify the proportion of filgotinib users with moderate to severe renal impairment being initiated on filgotinib at the recommended dose of 100 mg once daily
- To quantify the proportion of users of filgotinib who are being treated for active TB at the time of filgotinib treatment initiation and during follow-up (while continuing filgotinib treatment)
- To quantify the proportion of users of filgotinib who have a history of viral hepatitis at the time of filgotinib treatment initiation and during follow-up (while continuing filgotinib treatment)
- To quantify the proportion of female patients of childbearing potential who are pregnant at the time of filgotinib treatment initiation or become pregnant while continuing filgotinib treatment during follow-up
- To assess the proportion of filgotinib users receiving live, attenuated vaccines at the time of filgotinib initiation or at any time during follow-up while continuing filgotinib treatment
- To assess the proportion of filgotinib users with filgotinib discontinuation following a VTE event
- To describe prescribing physicians' adherence to recommendations for patient screening and laboratory monitoring (if available), specifically:
 - To assess the proportion of filgotinib users with evidence of having performed screening for TB prior to initiation of filgotinib
 - To assess the proportion of filgotinib users with evidence of having performed lipid monitoring 12 weeks after initiation of filgotinib
- To assess the proportion of filgotinib users with evidence of having performed the following laboratory tests prior to initiation of filgotinib: absolute neutrophil count (ANC), absolute lymphocyte count (ALC), hemoglobin (Hb) level

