8.3.1.1. ARTIS

Patient Baseline Characteristics

Baseline variables will include the following:

- Age (at baseline)
- Sex
- Renal impairment
 - Stage (if available)
- Date of initiation of filgotinib
- Initial dose of filgotinib
- First ever administration of filgotinib: y/n
- Previous RA treatment immediately prior to initiation of filgotinib
- Date of diagnosis of RA (year; approximate if greater than 10 years earlier)
- Current severity of RA
 - Disease Activity Score (DAS):
 - DAS for 28 joint count (DAS28)
 - DAS28 type: Erythrocyte Sedimentation Rate (ESR); C-reactive protein (CRP)
 - CRP value
 - ESR value
 - Health Assessment Questionnaire (HAQ) score
 - Visual analogue scale (VAS; patient assessment of disease)
 - RA type (seropositive, seronegative)
 - Date of assessment

Risk Factors for MACE, VTE, and Serious and Opportunistic Infections

As previously described, each registry was assessed for the availability of the set of potential risk factors for the 3 endpoints of concern. In ARTIS there are no measures of obesity or immobility, both risk factors for VTE, although HAQ could be used as a proxy.

Table 3 Risk Factors for MACE, VTE and Serious and Opportunistic Infections as Available in ARTIS

	MACE	VTE	Serious and Opportunistic Infections
History of cardiovascular disease	Yes		
History of VTE		Yes	
Previous serious infection			Yes
Age	Yes	Yes	Yes
Sex	Yes		
Diabetes type 1	Yes		Yes
Diabetes type 2	Yes		Yes
Atrial fibrillation	Yes		
Chronic kidney disease	Yes		Yes
Smoking	Yes	Yes	
Family history CVD	Yes		
Use of treatment: Hyperlipidemia (Dx unavailable)	Yes		
Use of treatment: Hypertension (Dx unavailable)	Yes		
Cancer diagnosis (date)	Yes	Yes	Yes
Known thrombophilic condition		Yes	
Reduced mobility / Hospitalization (date, type, length of stay)		Yes	
Trauma and/or surgery		Yes	

	MACE	VTE	Serious and Opportunistic Infections
Ongoing hormonal replacement therapy		Yes	
Heart and/or respiratory failure		Yes	
Acute myocardial infarction or ischemic strokes		Yes	
Chronic lung disease			Yes
Glucocorticoid			Yes
TNFi			Yes
Other immunosuppressant/modifying treatment			Yes

CVD = cardiovascular disease; Dx = diagnosis; MACE = major adverse cardiovascular event; TNFi = tumor necrosis factor inhibitor; VTE = venous thromboembolism

Physician Adherence

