In accordance with the RMP, SmPC and the description provided in Section 6.2, the following variables will be used to describe the adherence of the prescribing physician with respect to the Guide for HCP:

- Diagnosis of TB: yes/no
 - Date of diagnosis
- Diagnosis of herpes zoster: yes/no
 - Date of diagnosis
- Diagnosis of viral hepatitis: yes/no
 - Date of diagnosis
- Patient is currently pregnant (defined as greater than 25 weeks): yes/no
- Date of most recent full term pregnancy (for women aged <50 years old)
- Recent diagnosis of serious and opportunistic infection: yes/no
 - Type of infection
 - Date of diagnosis

Dose and age are already variables for this study and thus the use of 100 mg in patients aged ≥ 75 years old and in patients with chronic kidney disease can be addressed.

Concomitant Medication

The SmPC includes a warning that certain concomitant treatments should be avoided. Specifically, combination of filgotinib with other potent immunosuppressants such as azathioprine, ciclosporin, tacrolimus, biologic DMARDs, or other JAK inhibitors is not

recommended as a risk of additive immunosuppression cannot be excluded. For this reason, concomitant use will be recorded; this will not include any previous medication that is discontinued once filgotinib is first prescribed. Thus, this will capture those immunosuppressants that are prescribed to start with filgotinib or that are ongoing.

- Concomitant use of other immunosuppressant:
 - Type, name, and dose (incomplete)
 - Dates of dispensing

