8.3.1.2. BIOBADASER

Baseline characteristics captured by BIOBADASER are collected from the recruiting clinician or directly from each patient enrolled in the register using an electronic standardized form. The variables to be captured by the register are summarized in the following section.

Patient Baseline Characteristics

Baseline variables will include the following:

- Age (at baseline)
- Sex
- Renal impairment
- Date of initiation of filgotinib
- Initial dose of filgotinib
- First ever administration of filgotinib: y/n
- Previous RA treatment immediately prior to initiation of filgotinib
- Date of diagnosis of RA (year)
- Current severity of RA
 - Disease Activity Score (DAS):
 - DAS for 28 joint count (DAS28)
 - DAS28 type: ESR; CRP
 - CRP value
 - ESR value
 - VAS (patient assessment of disease)
 - RA type (seropositive, seronegative)
 - Date of assessment

Risk Factors for MACE, VTE, and Serious and Opportunistic Infections

As previously described, each registry was assessed for the availability of the set of potential risk factors for the 3 endpoints of concern.

Table 4 Risk Factors for MACE, VTE and Serious and Opportunistic Infections as Available in BIOBADASER

	MACE	VTE	Serious and Opportunistic Infections
History of CVD	Yes		
History of VTE		Yes	
Previous serious infection			Yes
Age	Yes	Yes	Yes
Sex	Yes		
Diabetes	Yes		Yes
Chronic kidney disease (stages 4, 5)	Yes		Yes
Smoking	Yes	Yes	
Hyperlipidemia	Yes		
Hypertension	Yes		
Active cancer & history of cancer		Yes	
Recent hospitalization		Yes	
Recent surgery		Yes	
Known thrombophilic condition		Yes	
Ongoing hormonal replacement therapy		Yes	
Heart and/or respiratory failure		Yes	
Acute myocardial infarction or ischemic strokes		Yes	
Obesity or BMI		Yes	
Acute infection and/or rheumatologic disorder		Yes	
Chronic lung disease			Yes

	MACE	VTE	Serious and Opportunistic Infections
Prior DMARD treatment failure			Yes
Glucocorticoid			Yes
TNFi			Yes

BMI = body mass index; CVD = cardiovascular disease; DMARD = disease-modifying antirheumatic drug; MACE = major adverse cardiovascular event; TNFi = tumor necrosis factor inhibitor; VTE = venous thromboembolism

Physician Adherence

In accordance with the RMP, SmPC and the description provided in Section 6.2, the following variables will be used to describe the adherence of the prescribing physician with respect to the Guide for HCP.

- Diagnosis of TB: yes/no
 - Date of diagnosis
- Diagnosis of herpes zoster: yes/no
 - Date of diagnosis

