8.3.1.3. BSRBR-RA

Patient Baseline Characteristics

Baseline variables will include the following:

- Age (at baseline)
- Sex
- Renal impairment
- Date of initiation of filgotinib
- Initial dose of filgotinib
- First ever administration of filgotinib: y/n
- Previous RA treatment immediately prior to initiation of filgotinib

- Date of diagnosis of RA (year)
- Current severity of RA
 - DAS:
 - DAS for 28 joint count (DAS28)
 - DAS28 type: ESR; CRP
 - CRP value
 - ESR value
 - HAQ score
 - VAS (patient assessment of disease)
 - RA type (seropositive, seronegative)
 - Date of assessment

Risk Factors for MACE, VTE, and Serious and Opportunistic Infections

A set of variables will be collected at baseline to define the risk of each of the 3 outcomes of concern: MACE, VTE, and serious and opportunistic infections (see definitions in Section 6.1 and Annex 4).

As previously described, each registry was assessed for the availability of the set of potential risk factors for the 3 endpoints of concern.

Table 6 Risk Factors for MACE, VTE and Serious and Opportunistic Infections as Available in BSRBR-RA

	MACE	VTE	Serious and Opportunistic Infections
History of CVD	Yes		
History of VTE		Yes	
Previous serious infection (partial availability)			Yes
Age	Yes	Yes	Yes
Sex	Yes		
Diabetes type 1	Yes		Yes
Diabetes type 2	Yes		Yes
Atrial fibrillation	Yes		
Chronic kidney disease (stages 4,5)	Yes		Yes
Smoking	Yes	Yes	

	MACE	VTE	Serious and Opportunistic Infections
Hyperlipidemia	Yes		
Hypertension	Yes		
Cancer and date of diagnosis		Yes	
Ongoing hormonal replacement therapy		Yes	
Acute myocardial infarction or ischemic strokes		Yes	
Obesity or BMI		Yes	
Chronic lung disease			Yes
Glucocorticoid			Yes
TNFi			Yes
Other immunosuppressant/modifying treatment			Yes

BMI = body mass index; CVD = cardiovascular disease; MACE = major adverse cardiovascular event; TNFi = tumor necrosis factor inhibitor; VTE = venous thromboembolism

Physician Adherence

In accordance with the RMP, SmPC and the description provided in Section 6.2, the following variables will be used to describe the adherence of the prescribing physician with respect to the Guide for HCP.

- Diagnosis of active TB: yes/no
 - Date of diagnosis
- Diagnosis of herpes zoster: yes/no
 - Date of diagnosis
- Diagnosis of viral hepatitis: yes/no
 - Date of diagnosis
- Previous opportunistic infection: yes/no
 - Date of diagnosis: yes/no
- Pregnancy: yes/no

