8.3.1.4. DANBIO

Patients are reported to the database at the time of diagnosis, referral to specialized treatment, including biological therapy at the hospital, or in a private rheumatologic clinic. At the first registration, the diagnosis, date of diagnosis, and other disease related variables (including previous DMARD treatments, anti-cyclic citrullinated peptide, and immunoglobulin M rheumatoid factor status, disease activity measures), socio demographic factors (age, sex), and health behavioral factors (including tobacco use) are registered.

The variables for the study will be collected at baseline; this is the date of each patient's first prescription/administration of filgotinib in the observational period. These variables reflect the patient's status at baseline (initiation of filgotinib) or the medical history prior to and including the baseline date. The variables to be captured by the register are summarized in the following section.

Patient Baseline Characteristics

Baseline variables will include the following:

- Age (at baseline)
- Sex
- Renal impairment
 - Current stage (1 to 5)
- Date of initiation of filgotinib
- Initial dose of filgotinib
- First ever administration of filgotinib: y/n
- Previous RA treatment immediately prior to initiation of filgotinib
- Date of diagnosis of RA (year)
- Current severity of RA
 - DAS28 CRP
 - HAQ score
 - VAS (patient assessment of disease)
 - RA type (seropositive, seronegative)

- Date of assessment

Risk Factors for MACE, VTE, and Serious and Opportunistic Infections

As previously described, each registry was assessed for the availability of the set of potential risk factors for the 3 endpoints of concern. With regards to serious and opportunistic infections, it is worth noting that DANBIO developed a risk score for infection (Krabbe et al., 2021). The risk factors considered are age, previous serious infection, pulmonary disease, diabetes and myocardial infarction and glucocorticoid use within the last year.

Table 7 Risk Factors for MACE, VTE and Serious and Opportunistic Infections as Available in DANBIO

	MACE	VTE	Serious and Opportunistic Infections
History of CVD	Yes		Yes
History of VTE		Yes	
Previous serious infection			Yes
Age	Yes	Yes	Yes
Sex	Yes		
Diabetes type 1	Yes		Yes
Diabetes type 2	Yes		Yes
Atrial fibrillation	Yes		
Smoking	Yes	Yes	
Hyperlipidemia	Yes		
Hypertension	Yes		
Active cancer & history of cancer		Yes	
Known thrombophilic condition		Yes	

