
Hyperlipidemia
	
BIOBADASER: Lipid measures LDL, HDL, total cholesterol or triglycerides may be captured according to clinical practice.
	
Patients who will initiate treatment with statins and other lipid-lowering drugs.

	
BSRBR-RA: Patients who will initiate treatment with statins or other lipid-lowering drugs.
 
RABBIT: Hyperlipidemia reported as adverse event by the treating physician.
	
--	--	--

Other medical history

Disease	Data source	ICD10
Malignancy	The Cancer register	All except benign tumors
Infection	Main diagnoses from the Inpatient component of Patient Register.	A00B99, D73.3, E06.0, E32.1, G00G02, G04.2, G05G07, H00.0, H44.0, H60.0H60.3, H66H67, H70, I30.1, I40.0, J00J22, J32, J34.0, J36, J38.3, J39.0J39.1, J44.0, J85, J86, K04.4, K04.6, K04.7, K10.2, K11.3, K12.2, K14.0, K57.0, K57.2, K57.4, K57.8, K61, K63.0, K65.0, K65.1, K65.2, K65.9, L00L08, L30.3, M00M01, M46.2M46.5, M60.0, M65.0, M71.0, M71.1, M72.6, M86, N10, N11, N12, N13.6, N15.1, N15.9, N30.0 N30.8, N34.0, N41.2, N43.1, N45.2, N45.3, N45.4, N48.2, N61, N70, N73, N75.1
Renal impairment		N18, N18.1, N18.2, N18.3, N18.4, N18.5
Knee or hip prosthesis	Operation codes from the Patient register	NGB, NFB
Diabetes	The Patient Register	E10E14, O24
Myocardial infarction	The Patient Register	I21, I22

SIGNATURE PAGE – INVESTIGATOR

Study Title: Non-interventional post-authorization cohort safety study evaluating the effectiveness of the additional risk minimization measures for filgotinib (Jyseleca®) use in patients with moderate to severe active rheumatoid arthritis within European registries

CSP Version:

1.0

Date:

02-Feb-2022

I, the undersigned, have read this non-interventional study protocol and will conduct the study as described in compliance with the study protocol, in accordance with the guidelines of Good Pharmacoepidemiology Practises and Heads of Medicines Agencies Good Pharmacovigilance Practices.

Investigator Name

Signature

Date

SIGNATURE PAGE – SPONSOR

Study Title: Non-interventional post-authorization cohort safety study evaluating the effectiveness of the additional risk minimization measures for filgotinib (Jyseleca®) use in patients with moderate to severe active rheumatoid arthritis within European registries

CSP Version: 1.0 **Date:** 02-Feb-2022

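### The renal dose objective concerns stages 3-4, but no registry section ties its denominator to those stages, and in BIOBADASER and BSRBR-RA the only staged variable covers stages 4-5

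*Protocol*

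**What the plan says.** Section 7 states the objective as the proportion of "filgotinib users with moderate to severe renal impairment being initiated on filgotinib at the recommended dose of 100 mg once daily". Section 6.1 says who that is: "moderate or severe renal impairment (stages 3 or 4; creatinine clearance [CrCl] 15 to <60 mL/min". Section 6 gives the same creatinine clearance range.

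The registry sections (8.3.1.1 to 8.3.1.5) each close their physician-adherence list with the same remark. Dose and age are already study variables, so the use of 100 mg "in patients with chronic kidney disease can be addressed". No stage or creatinine clearance limit is attached to that remark in any of the five.

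Annex 4, under other medical history, lists renal impairment as "N18, N18.1, N18.2, N18.3, N18.4, N18.5". The data-source cell for that row is empty, and no subset is named for the dose objective.

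**The concern.** The objective has a defined target group, and the text that makes it operational uses a wider, differently named one. If the analysis follows the registry sections as written, the reported share on 100 mg describes whatever each registry can call chronic kidney disease.

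Two errors are then possible, in opposite directions. Patients outside stages 3-4 can enter the denominator, and if they are less often started on 100 mg, adherence looks worse than it is. Where stage 3 is not captured, any departure from the recommendation in that stage is not seen, and adherence can look better than it is.

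This is one of only two dose objectives in a study meant to judge whether the risk minimization measures work. The consolidated report goes to the EMA and the MHRA (Section 11.1). Figures from different populations under one label could mislead there.

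**Working it through.** The protocol gives no count, proportion or precision for the renal objective, so there is no figure to reproduce. Section 8.5 covers contraindication and high-risk proportions only. The check is a comparison of definitions.

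**Step 1. Target set.** From Sections 7 and 6.1: stages {3, 4}.

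**Step 2. What each registry section shows.**

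| Registry | Renal item in baseline list | Row in risk-factor table | Stages 3-4 identifiable from the text? |
|---|---|---|---|
| ARTIS | Renal impairment, "Stage (if available" | Chronic kidney disease, no stage (Table 3) | Only where stage is recorded |
| BIOBADASER | Renal impairment, no stage | "Chronic kidney disease (stages 4, 5" (Table 4) | Not shown |
| BSRBR-RA | Renal impairment, no stage | "Chronic kidney disease (stages 4,5" (Table 6) | Not shown |
| DANBIO | Renal impairment, "Current stage (1 to 5" | No kidney row (Table 7) | Yes |
| RABBIT | Renal impairment, no stage | Chronic kidney disease, no stage (Table 8) | Not shown |

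**Step 3. Compare the sets.** For BIOBADASER and BSRBR-RA, {4, 5} against {3, 4} shares only stage 4, misses stage 3 and adds stage 5. For the Annex 4 list, if the decimal is read as the stage (an assumption, since the document does not say so), the list adds stages 1, 2 and 5 and unstaged disease, but N18.3 and N18.4 appear as separate codes and can be selected.

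**Step 4. Can the gap be closed later?** Section 8.3.1 says the registry tables reflect which variables are available. The milestone footnotes say the registries' data fields are fixed. Section 8.3.1.2 says BIOBADASER alone can add data collection screens, and its added variables (Table 5) include neither creatinine nor kidney disease stage. On the protocol's own account, no planned source supplies a stage 3 flag in BIOBADASER, BSRBR-RA or RABBIT.

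**Step 5. Illustration of direction only.** Every input here is assumed; none is in the document.

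- *Denominator too wide.* Let f be the share of the denominator in stages 3-4, a the 100 mg use in that group, and b the use outside it. Reported = f·a + (1 − f)·b. With a = 0.90, f from 0.5 to 0.9 and b from 0.10 to 0.30, the lowest value is 0.5 × 0.90 + 0.5 × 0.10 = 0.50 and the highest is 0.9 × 0.90 + 0.1 × 0.30 = 0.84, against a true 0.90. The error is (1 − f)(b − a), which shrinks to zero as b approaches a.
- *Stage 3 not seen.* Let s be the share of stage 3 within stages 3-4. True = s·a3 + (1 − s)·a4. With a4 = 0.90, a3 from 0.50 to 0.80 and s from 0.5 to 0.9, the lowest value is 0.9 × 0.50 + 0.1 × 0.90 = 0.54 and the highest is 0.5 × 0.80 + 0.5 × 0.90 = 0.85. A figure from stage 4 alone would read 0.90. Stage 5 patients are ignored here.

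**The case against.** Several counter-arguments have force.

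- *A reader might infer that every registry uses the wrong stages.* The documents do not support that. DANBIO records stages 1 to 5, ARTIS records stage where it can, and RABBIT lacks a stage but does not have a wrong one.
- *A reader might take the Annex 4 list as the dose denominator.* It is a medical-history code list, in an annex whose lists were created for the separate long-term safety study. It identifies renal impairment of any degree and nothing says all its codes form this denominator. In the annex's main table, ICD-10 codes apply only to ARTIS and DANBIO, so the list cannot show an error in all five registries.
- *A reader might infer that every stage 3 patient is lost in BIOBADASER and BSRBR-RA.* The stages 4-5 label sits in the MACE and infection columns of the risk-factor tables, and both registries also list a renal impairment item with no stage limit. That item may include stage 3 patients. Loss of the whole group is not established. What stands is that nothing shown separates stages 3-4 from the rest.
- *Selecting a stage subset is ordinary SAP content, and Section 8.7 defers detailed methods.* This is right for DANBIO and for staged ARTIS records. It does not help where no stage is recorded, because an analysis plan cannot create one.
- *No pooled renal figure is specified, and Section 8.9 admits that some information may not be captured by all registries.* True, but a consolidated report is planned, and the general caveat does not mention kidney disease stage. The sentence in each registry section says the opposite.
- *The dilution may be small.* Patients aged 75 or over have a recommended starting dose of 100 mg whatever their renal stage, so use outside stages 3-4 could be well above the 10-30% assumed in the illustration. This is why no size is claimed.

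**Conclusion.** The point holds in a limited form. The renal dose objective is defined by stages 3 or 4, and that definition is not carried into any registry section. The statement that the check can be addressed is unsupported, on the text shown, for BIOBADASER, BSRBR-RA and RABBIT. It is conditional on recorded stage for ARTIS. It is achievable in DANBIO if the denominator is restricted.

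The size of the bias cannot be derived from the document. The ranges under the illustration show only that the two mechanisms can push in opposite directions, and they should not be cited as estimates. The conclusion rests on reading the registry tables as statements of what is available, which is how Section 8.3.1 describes them. No view is taken on the dose or the renal cut-off.

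**What to change.** Reconcile Sections 6.1 and 7 with Sections 8.3.1.1 to 8.3.1.5 and Annex 4 by tying the denominator to the protocol's own stage 3-4 definition.

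- **DANBIO, and ARTIS where stage is recorded:** restrict the denominator to stages 3-4 and show unstaged records in a separate row.
- **BIOBADASER, BSRBR-RA and RABBIT:** state whether stages 3-4 can be identified, and from which variable. If they cannot, label the result by what is captured (*stages 4-5 only* or *stage unknown*) and do not present it in the consolidated report as the moderate-to-severe figure.
- **All registries:** replace the shared sentence with a registry-specific statement of what can be measured.
- **Annex 4:** note that the renal list identifies any renal impairment, and name the subset used for this objective.

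The cost is edits to text, code lists and table footnotes. The downside is smaller denominators, and an objective that may be shown as not estimable in some registries.
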